12.7.4.1 Total costs

Cost effectiveness will be estimated comparing the costs for each regimen. A cost-effectiveness ratio will be calculated as [Costs associated with preemptive therapy- costs associated with prophylaxis]/Effect of preemptive therapy-effect prophylaxis therapy]. Where the costs are the total composite costs derived from the analysis tree and the effect is CMV disease free success.

12.7.4.2 Cost utility analysis

A Cost-utility analysis will estimate the cost per quality-adjusted life-years (QALY). Quality of life will be estimated for possible outcomes where 0=death and 1=perfect health. The utility values will be estimated from the literature for patients with end stage liver disease and cirrhosis (74, 75). A fully functioning graft at one year, in a recipient with no major complications is estimated to have a utility value of about .83. Utility values for subjects with complications will be estimated from articles listed in the Cost-effectiveness analysis registry (76). Cost per QALY will be estimated for both regimens.

Cost utility analysis is based on estimated utilities found in the literature for items already collected such as retransplantation/disease/death. No additional data items will be collected.

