12.4.5 Duration of treatment, compliance, and participation

Duration of valganciclovir, length of study participation (while on therapy and during follow up), compliance as well as a distribution of the number of days from the date of transplantation to the date of the first dose of valganciclovir [prophylaxis arm] or date of first CMV PCR test [preemptive arm] will be summarized for the modified ITT population using descriptive statistics, including frequency distributions. For the preemptive arm the number of PCR tests, number of days between positive PCR test and the initiation of valganciclovir as well as the exposure to valganciclovir will be summarized.

Duration of valganciclovir is (date of the last dose of drug minus the date of first dose of drug plus 1 day).

Study participation as defined by the duration of the overall CMV evaluation period (while on therapy and during follow-up) will be summarized for the ITT and modified ITT populations. Evaluation period length for CMV disease assessment is (date of last study contact minus the date of randomization plus 1 day).

Receipt and duration of generic or nongeneric valganciclovir will be recorded and summarized for each study population.

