12.7.4 Cost effectiveness analysis

CMV disease and the costs associated with treating it are estimated to add \$25,000 to \$50,000 to the cost of organ transplantation (70, 71). In addition to the direct effects of CMV disease, CMV in transplant recipients may contribute to an increased risk of rejection and opportunistic infection (OI). These events add a substantial economic burden to solid organ transplantation related to diagnosis, treatment and increased hospital length of stay. In addition to the economic considerations, CMV may also reduce graft and recipient survival. Treeage Pro 2009 [Treeage software, Williamstown, MA] will be used to develop a decision analysis model. The basic model will be similar in structure to those developed by Mauskopf et.al (72) for evaluating CMV in renal transplantation and Annemans et.al.(73) in liver transplantation. The tree will be utilized to estimate the costs associated with the 2 CMV intervention strategies, preemptive therapy and prophylaxis. Each strategy has the principle outcome of CMV disease, no disease. The disease state (CMV disease/no CMV disease) then transitions to 4 possible outcome states: rejection, OI, both rejection and OI, or no complications. Rejection can then transition to graft loss/no loss. Each outcome state terminates as alive/dead. Transition probabilities will be estimated post hoc. The model will allow for a range of sensitivity analyses

in which the parameter estimates can be varied [for example at the 10th and 90th percentile of the observed value].

Data already collected in this study will be used for cost effectiveness analyses. These include length of stay, drugs received for CMV prophylaxis/preemptive therapy, CMV disease, treatment for leukopenia, and other outcomes including rejection and retransplantation. Available data already captured will be used for the analyses; no additional items will be collected specifically for costs efficacy analyses. Cost estimates are obtained from average standard costs for drugs and procedures available in the literature. No site specific costs will be collected.

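### The exploratory cost-utility analysis states only a cost per QALY for each regimen and no incremental cost per QALY or net benefit, and it leaves the costing of PCR monitoring unspecified

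*Combined protocol and SAP*

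**What the plan says.** Section 12.7.4 describes one decision tree with two outputs.

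- **Cost-effectiveness (12.7.4.1).** This is a between-arm measure: "A cost-effectiveness ratio will be calculated as [Costs associated with preemptive therapy- costs associated with prophylaxis]/Effect of preemptive therapy-effect prophylaxis therapy". Its denominator is not in QALYs, because "the effect is CMV disease free success".
- **Cost-utility (12.7.4.2).** The stated output is "Cost per QALY will be estimated for both regimens". The section gives no difference between arms in cost or QALYs, no net benefit, no dominance rule and no threshold.

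On cost inputs, 12.7.4 relies on data the trial already collects: "These include length of stay, drugs received for CMV prophylaxis/preemptive therapy, CMV disease, treatment for leukopenia, and other outcomes including rejection and retransplantation". CMV PCR is not named. The stated scope is wider than that list, however: "The tree will be utilized to estimate the costs associated with the 2 CMV intervention strategies, preemptive therapy and prophylaxis", and "Cost estimates are obtained from average standard costs for drugs and procedures available in the literature". Test counts will be available, since 12.4.5 summarises, among other things, "For the preemptive arm the number of PCR tests".

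Section 7.5.3.2 restricts surveillance PCR to the preemptive arm, and Appendix B counts 14 such visits. Cost effectiveness is an exploratory objective (3.1.3). Section 12.8.2 cites it among the reasons to continue even if the interim analysis shows the arms to be equivalent on CMV disease.

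**The concern.** The question for a cost-utility comparison is whether the extra cost of one strategy is justified by the extra QALYs it yields. That needs the difference in cost and the difference in QALYs. A cost per QALY for each arm divides each arm's total cost by its total QALYs, so most of both quantities is common to the two arms and the comparison of interest is hidden. If a reader ranks the regimens by these two ratios, the order can be the opposite of the one that net benefit gives.

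The second, smaller issue concerns cost items. Weekly PCR is what makes preemptive therapy work, and only that arm receives it as surveillance. If the analyst credits that arm with less drug and less disease but does not charge it for the tests, its cost is understated. The text leaves this open.

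**Working it through.** **1. The plan's own count.** Surveillance days run from 7 to 98 in steps of 7, so 98/7 = 14 tests. At 8.5 ml each, 14 × 8.5 = 119 ml, which matches Appendix B. The number is higher for subjects still on treatment after day 98 (7.5.3.2).

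**2. Average against incremental ratios.** Let C0 and Q0 be the mean cost and QALY for prophylaxis, and C1 and Q1 those for preemptive therapy. The documents give none of these, so the values below are assumptions chosen to show the mechanism.

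| | Prophylaxis | Preemptive |
|---|---|---|
| Mean cost | $20,000 | $22,000 |
| Mean QALY | 0.78 | 0.83 |
| Average ratio, C/Q | 20,000/0.78 = $25,641 | 22,000/0.83 = $26,506 |
| Net benefit at $50,000 per QALY | 50,000 × 0.78 − 20,000 = $19,000 | 50,000 × 0.83 − 22,000 = $19,500 |

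The incremental ratio is (22,000 − 20,000)/(0.83 − 0.78) = 2,000/0.05 = $40,000 per QALY. The averages put prophylaxis first. At any threshold above $40,000, net benefit puts preemptive therapy first. Below $40,000 the two methods agree.

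In general, when preemptive therapy costs more and yields more, the averages misrank it whenever the incremental ratio lies above C0/Q0 but below the threshold. Here that is $25,641 < $40,000 < $50,000. If instead C1 < C0 and Q1 > Q0, then C1/Q1 < C0/Q0, and the averages rank correctly.

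**3. Size of the PCR item, if it were left out.** The plan gives no unit cost. At an assumed $50 to $400 per test, the understatement per preemptive subject with the 14 scheduled tests is 14 × 50 = $700 to 14 × 400 = $5,600.

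*At the design rates.* Section 12.1 assumes 20% and 5% disease, and 12.7.4 puts the added cost of CMV disease at $25,000 to $50,000. The disease saving is 0.15 × 25,000 = $3,750 to 0.15 × 50,000 = $7,500 per subject. Before any drug saving is counted, omission reverses the sign of the cost difference only if a test costs more than 3,750/14 = $268 to 7,500/14 = $536.

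*At equal disease rates.* The disease saving is zero, and the main offset is the 43% lower drug use estimated in 2.2.2. Assume full-dose prophylaxis, no renal adjustment, and the 43% applied to tablets. Then 900 mg daily in 450 mg tablets for 100 days is 200 tablets, and 43% of that is 86 tablets. Omission reverses the sign of this drug-against-PCR balance when one test costs more than 86/14 = 6.1 tablets. With assumed prices:

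| Tablet | Test | Preemptive minus prophylaxis, PCR omitted | PCR included |
|---|---|---|---|
| $5 | $100 | −$430 | −430 + 1,400 = +$970 |
| $20 | $100 | −$1,720 | −1,720 + 1,400 = −$320 |
| $20 | $200 | −$1,720 | −1,720 + 2,800 = +$1,080 |

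The sign reverses in two of these three cases.

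**The case against.** The sponsor has a fair reply on several counts, and four stronger readings should be set aside.

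- A reader might infer that the whole economic analysis rests on average ratios. It does not: 12.7.4.1 is incremental. Only the QALY output lacks a between-arm measure.
- A reader might infer that PCR cost has been excluded and that the plan therefore favours preemptive therapy. No such exclusion is written. The item list is open-ended, the tree covers the costs of both strategies, unit costs extend to procedures, and the test count is captured. Any bias is conditional on the item being left out.
- A reader might infer that PCR is the only resource specific to the preemptive arm. Section 6.2.2.2 also gives that arm acyclovir for at least 28 days.
- A reader might infer that a wrong ranking is the likely result. The design assumptions (20% against 5% disease, 43% less drug) point towards preemptive therapy being both cheaper and more effective, and averages then rank correctly. Setting PCR cost against the disease saving alone would also overstate its weight, because the drug saving counts too.

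It can also be said that 12.7.4.2 never calls the two ratios a decision rule, and that a tree giving each arm's cost and QALY yields the increment by subtraction. Both are true. They show that the remedy is easy, but they do not supply the missing measure: the section as written still ends with two averages and no comparison.

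**Conclusion.** The point holds for the cost-utility analysis in 12.7.4.2. Its only stated output is a ratio for each regimen, which can give the wrong order when one strategy both costs more and yields more QALYs. The incremental form that 12.7.4.1 already uses is better and costs nothing in data. The $25,641 against $26,506 example rests on assumed costs, QALYs and threshold; it shows that misranking can happen, not that it is expected here.

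The PCR part is a clarification. Omission would understate preemptive cost by 14 times the unit cost for a subject who completes scheduled surveillance, and by more if testing continues. It would matter most if disease rates proved similar, which is the situation in which 12.8.2 relies partly on cost effectiveness to justify continuing. Section 12.8.2 gives other reasons too, and the endpoint is exploratory, so no primary or secondary conclusion depends on this.

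**What to change.** In 12.7.4.2, state that the between-arm result is the incremental cost per QALY (difference in mean cost divided by difference in mean QALY), or the incremental net benefit over a stated range of thresholds. Apply the sensitivity ranges already planned in 12.7.4. Keep the per-regimen ratios as descriptive output only.

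In the same edit to 12.7.4, name two cost items: surveillance PCR in the preemptive arm, as the observed number of tests per subject times a literature unit cost, and PCR for suspected CMV disease in both arms (7.6.4). Vary the unit cost in the sensitivity analysis.

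The cost is a few sentences in the SAP, one literature unit cost and slight extra analysis. No additional data are collected. The cost result for preemptive therapy may become less favourable.

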12.8 Interim and Final Analysis

12.8.1 Interim analysis

There will be a single planned interim analysis for the primary endpoint of CMV disease. This analysis will be done after 1/3 of the subjects or 60 subjects have been enrolled and followed for 1 year. Additional endpoint analysis would introduce a multiple comparison bias with a resultant "alpha penalty". Each test done at $\alpha=.05$ means that roughly 5% will generate a type 1 error [rejecting the null hypothesis when in fact it is true]. Repeated testing of interim data can therefore inflate false positive error. To account for this loss of alpha, the sample size would need to be up-adjusted making the study infeasible. For the planned interim analysis, we will use alpha preservation estimation for repeated assessments [Method of

Haybittle-Peto] so that the trial will be terminated only if there is a statistically significant difference in the incidence of CMV disease at the 0.001 level. A statistically significant difference in the incidence of CMV disease at this level [.001] would be detectable after the enrollment of 60 subjects with 1 year follow up, if the difference in the incidence of CMV diseases between the two groups is greater than 50%.

12.8.2 Interim analysis showing futility:

It is possible that the interim analysis could suggest the likelihood of futility i.e. the trial may result in equivalence or non-inferiority. However, there will be no stopping rule for futility. Even if the interim analysis shows that the two groups are equivalent in efficacy with regards to CMV disease rate, there are additional benefits of continuing the trial for example, cost effectiveness of the two approaches which has societal benefits and wider implications. Additionally, differences in immunologic parameters, opportunistic infections, survival, graft loss, and drug resistance have profound relevance for advancing the field. The study will therefore continue so that these additional assessments can be systematically conducted.

12.8.3 Final analysis:

This will be completed when all subjects who have not previously discontinued have completed the one year follow up study visit. Primary, secondary and selected exploratory analyses (outlined in section 12.7) will be performed after one year follow up with supplementary analyses of exploratory endpoints (outlined in section 12.7) performed at study closure (and no longer than 7 years after first enrollment).

13 SOURCE DOCUMENTS AND ACCESS TO SOURCE DOCUMENTS

Source data for CAPSIL are defined as all the information related to clinical findings, observation, or other activities in the study, written down or electronically entered in original records

In addition, medical records and laboratory data from all facilities (long-term nursing care facilities, rehab institutions, out-patient clinics) where subjects receive care throughout the study will be reviewed and serve as source documentation. Records to include all physician progress notes, laboratory results, diagnostic testing results, and medication records, will be requested from the institutions by the enrolling site for review and monitoring purposes.

Additionally, study specific source documents have been created to record data not routinely documented in the subject's medical record. Study specific documents created for the CAPSIL study. For each subject entered into the study, the investigator will keep a file that will record the specific data which are not part of the routine documentation. The investigator will permit trial-related monitoring, audits, IRB reviews, and regulatory inspections by providing direct access to source data according to the subject's consent.

Each participating site will maintain appropriate medical and research records for this trial, in compliance with ICH E6, Section 4.9 and regulatory and institutional requirements for the protection of confidentiality of subjects. Each site will permit authorized representatives of the DMID, its designees, and appropriate regulatory agencies to examine (and when required by applicable law, to copy) clinical records for the purposes of quality assurance reviews, audits, and evaluation of the study safety and progress. These representatives will be permitted access to all source data for CAPSIL study. Participating sites should consult the MOP and the DMID/NIAID Source Document Standards for specific instructions/forms.

14 QUALITY CONTROL AND QUALITY ASSURANCE

Following a written DMID-accepted site quality management plan, the investigational site is responsible for conducting routine quality assurance (QA) and quality control (QC) activities to internally monitor study progress and protocol compliance. The Principal Investigator will provide direct access to all trial-related sites source data/documents, data collection forms, and reports for the purpose of monitoring and auditing by the sponsor, and inspection by local and regulatory authorities. The Principal Investigator will ensure all study personnel are appropriately trained and applicable documentations are maintained on site. DMID-designated clinical monitors will verify that the clinical trial is conducted and data are generated, documented (recorded), and reported in compliance with the protocol, Good Clinical Practice, and the applicable regulatory requirements. Clinical monitoring reports will be submitted to DMID.

The Statistical and Data Coordinating Center will implement quality control procedures beginning with the data entry system and generate data quality control checks that will be run on the database. Any missing data or data anomalies will be communicated to the site(s) for clarification and resolution.

15 ETHICS/PROTECTION OF HUMAN SUBJECTS

15.1 Ethical Standard

The investigator will ensure that this study is conducted in full conformity with the principles set forth in The Belmont Report: Ethical Principles and Guidelines for the Protection of Human Subjects of Research of the US National Commission for the Protection of Human Subjects of Biomedical and Behavioral Research (April 18, 1979) and codified in 45 CFR Part 46 and/or the ICH E6; 62 Federal Regulations 25691 (1997).

15.2 Institutional Review Board

Reviewing IRBs will be registered with the OHRP to conduct FDA-regulated studies. In the United States and in other countries, only institutions and will hold a current US Federal wide Assurance (FWA) issued by OHRP. Notification of the IRB's composition and the institutions FWA number will be provided to DMID. This protocol, informed consent documents, relevant supporting information, and all types of volunteer recruitment or advertisement information will be submitted to the Institutional Review Board (IRB) for review and must be approved before the study is initiated. Any amendments to the protocol must also be approved by the IRB prior to implementing changes in the study. The investigator is responsible for keeping the IRB apprised of the progress of the study and of any changes made to the protocol as deemed appropriate, but in any case at least once per year. The investigator must also keep the IRB informed of any significant AEs. All IRB approved documents as well as relevant study correspondence should be copied and sent to U. Pitt (Coordinating Center).

15.3 Informed Consent Process

The process of obtaining informed consent must be documented in the medical records, clinic chart, and/or research chart. The consent form must be signed and dated by the study participant or legal guardian before participation in the study. A copy of the signed consent form must be provided to the study participant or legal guardian. Signed consent forms must remain in each study participants study file and must be available for verification by study monitors at any time.

The investigational nature and research objectives of this trial, the procedure, and its attendant risks and discomforts will be carefully explained to the study participant or legal guardian. A signed informed consent document will be obtained from each study participant or legal guardian prior to entry into this study. At any time during participation in the protocol, if new information becomes available relating to risks, AEs, or toxicities, this information will be provided orally or in writing to all enrolled or prospective study participant or legal guardian.

Documentation will be provided to the IRB and, if necessary, the informed consent will be amended to reflect any relevant information.

An investigator shall seek such consent only under circumstances that provide the prospective subject or the representative sufficient opportunity to consider whether or not to participate and that minimize the possibility of coercion or undue influence. The information that is given to the subject or the representative shall be in language understandable to the subject or the representative.

The participant or legal guardian will sign the informed consent document prior to any procedures being done specifically for the study. The participant or legal guardian should have the opportunity to discuss the study with their family, friends or personal physician, or think about it prior to agreeing to participate. The participant or legal guardian may withdraw consent at any time throughout the course of the trial. A copy of the informed consent document will be given to the participant or legal guardian for their records. The rights and welfare of the subjects will be protected by emphasizing to them that the quality of their medical care will not be adversely affected if they decline to participate in this study.

For non-English speaking subjects, a translated informed consent form will be used according to institutional IRB specific procedures.

15.4 Exclusion of Women, Minorities and Children (Special Populations)

Subjects will be eligible for participation in the study, regardless of gender, race or ethnicity. All patients undergoing liver transplant are potentially eligible for inclusion. The expected percentage of women and minorities enrolled will reflect the local demographics of the liver transplant population. Only individuals who are greater than or equal to 18 years old will be included at this time.

Children will not be included in the trial because there are significant problems and concerns with the use and appropriate dosing of valganciclovir in pediatric setting. Unlike adult transplant recipients, the oral bioavailability of valganciclovir is considerably lower in children (77). Its use in pediatric patient population has been limited by low bioavailability necessitating large and frequent doses, a problem compounded by the increased weight-adjusted clearance of ganciclovir in children (78). Consequently, unexpectedly high inter- and intrapatient variability in ganciclovir levels has been observed (77) and dosing recommendations based on adult guidelines have the potential for overdosing in children with below normal serum creatinine, low body surface area or low body weight. The potential dosing variability in pediatric subjects could significantly confound the study. Thus, there are significant concerns related to the potential for inadvertently achieving low levels and the risk of ganciclovir resistance.

A powder for oral solution with bioequivalence to valganciclovir tablets exists (78). However, valganciclovir oral solution in pediatric liver and kidney transplant recipients using a dosing algorithm based on dose normalization for body surface area resulted in children aged <5 years being under exposed to ganciclovir by approximately 2-fold (79-80). Another study (WV 16726) that included 63 pediatric transplant recipients of whom 17 were liver

transplant patients assessed the pharmacokinetic, safety, and efficacy study of the valganciclovir oral solution using dosing algorithm based on creatinine clearance and body surface area (81). A majority of the patients (60%) belonged to groups other than R-/D+. Treatment failures defined as either the development of CMV disease up to day 100 post-transplant or discontinuation of study medication due to lack of efficacy or toxicity was observed in 7% of the patients; a higher number of these were liver transplant recipients. When only R-/D+ patients were considered, treatment failure was documented in 33%. Currently, oral solution is not approved for use in pediatric liver transplant recipients.

While, there are recipes available to compound liquid valganciclovir from the tablets, there is no standardization for these. Furthermore, unlike adult liver transplant recipients, there are very limited published data on the use of oral valganciclovir in children and there is no precedence for the use of valganciclovir as preemptive therapy in children (11). Given low bioavailability and the potential for erratic drug levels, use of valganciclovir for established viremia as in the setting of preemptive therapy is a major concern. Prolonged valganciclovir use in the form of prophylaxis is also theoretically worrisome given the known carcinogenicity in animals and unknown consequences of prolonged ganciclovir derivatives in children.

Thus, valganciclovir use in children in context of this study poses compelling and significant concerns related to bioavailability (with the potential for both underdosing and overdosing), efficacy and toxicity such that the scientific validity of the study results and the safety of the subjects could be compromised. Therefore until further data becomes available regarding the safety and appropriate dosing of valganciclovir, inclusion of children in this study was not deemed prudent.

